14.4 Clinical laboratory assays

14.4.1 *Hematology, blood chemistry, urine analysis*

Samples of blood (12 mL) and urine will be collected. The following laboratory analyses will be performed at the screening visit:

Hematology

Leukocytes and leukocyte differential count, erythrocytes, hemoglobin, hematocrit, MCV, MCH, MCHC, thrombocytes.

Blood chemistry

Electrolytes: sodium, potassium, calcium, chloride, inorganic phosphorus

Enzymes: alkaline phosphatase, γ -GT, AST, ALT

Substrates/metabolites: total bilirubin, creatinine, glucose, urea, uric acid, total cholesterol, triglycerides

Proteins: total proteins

Serum pregnancy test (women): serum b-HCG test.

Urine analysis

Urine chemical analysis (stick): pH, specific weight, appearance, color, nitrites, proteins, glucose, urobilinogen, bilirubin, ketones, hematic pigments, leukocytes

Urine sediment (analysis performed only if positive): leukocytes, erythrocytes, flat cells, round cells, crystals, cylinders, mucus, bacteria, glomerular erythrocytes

The same analyses, except for the pregnancy test, will be performed at the final visit / ETV of Part A and, in Part B, at the end of period 1 (Day 13) and on Days -1 and 11 (corresponding to the Final visit/ETV) of period 2.

14.4.2 *Serum virology*

Hepatitis B (HBs antigen), **Hepatitis C** (HCV antibodies), **HIV 1/2** (HIV Ag/Ab combo) will be assayed at the screening visit in both study Parts.

14.4.3 Urine drug test

A urine drug test will be performed at the Phase I Unit at screening of both study Parts, using a urine multi-drug test kit. The test will be repeated upon confinement on Day -1 of Part A and in both periods of part B.

14.4.4 Pregnancy tests

A serum pregnancy test will be performed at the clinical laboratory (7.4) at screening of both Parts.

Urine pregnancy tests will be performed at the Phase I Unit on Day -1 and Final visit / ETV in Part A and on Day -1 and 13 of period 1 and Day -1 and 11 of period 2 in Part B (Test on Day 11 of period 2 corresponding to the Final visit / ETV test).

14.4.5 Data management

Date/time of samples collections, overall Investigator's interpretation (as normal or abnormal and, if abnormal, clinically significant or not clinically significant) and clinically significant findings (if any) will be reported in the individual CRFs. All clinically significant abnormalities after the screening visit will be recorded as AEs. Hard copies of the laboratory print-outs will be attached to the CRFs.

14.5 Sampling for pharmacokinetic analysis

14.5.1 Venous blood sampling

Venous blood samples will be collected from a forearm vein through an indwelling catheter or venipuncture at the times summarized in the following table. All blood samples will be withdrawn from the contralateral arm with respect to the arm used for the injection/infusion. The indwelling catheter will be removed at the end of the confinement or before in case of need.

Table 14.5.1.1 Schedule of PK blood sampling

		Blood sampling times after the start of T or R treatment									
		T injection of						Reference product infusion of			
		2 min		5 min		15 min		30 min		30 min	30 min
		Part A	Part B	Part A	Part B	Part A	Part B	Part A	Part B	Part A (Ra)	Part B (R)
Pre-dose	X	X		X	X	X	X	X	X	X	X
2 min	X	X									
5 min	X	X	X	X							
10 min	X	X	X	X							
15 min	X	X	X	X	X	X					
20 min	X	X	X	X	X	X					
30 min	X	X	X	X	X	X	X	X	X	X	X
45 min	X	X	X	X	X	X	X	X	X	X	X
1 h	X	X	X	X	X	X	X	X	X	X	X
1.5 h	X	X	X	X	X	X	X	X	X	X	X
2 h	X	X	X	X	X	X	X	X	X	X	X

		Blood sampling times after the start of T or R treatment									
		T injection of								Reference product infusion of	
		2 min		5 min		15 min		30 min		30 min	30 min
		Part A	Part B	Part A	Part B	Part A	Part B	Part A	Part B	Part A (Ra)	Part B (R)
3 h	X	X	X	X	X	X	X	X	X	X	X
4 h	X	X	X	X	X	X	X	X	X	X	X
8 h	X	X	X	X	X	X	X	X	X	X	X
12 h	X	X	X	X	X	X	X	X	X	X	X
24 h	X	X	X	X	X	X	X	X	X	X	X
48 h		X		X		X		X			X
72 h		X		X		X		X			X
96 h		X		X		X		X			X
120 h		X		X		X		X			X
144 h		X		X		X		X			X
168 h		X		X		X		X			X
192 h		X		X		X		X			X
216 h		X		X		X		X			X
240 h		X		X		X		X			X

T = Fosnetupitant 235 mg in 20 mL IV injectable solution administered at predefined time durations (30, 15, 5 and 2 min);

R = Fosnetupitant/palonosetron 235 mg/0.25 mg (IV Akynezo FDC) 20 mL liquid formulation diluted to 50 mL and administered in 30 min (Part B);

Ra = Fosnetupitant/palonosetron 235 mg/0.25 mg (IV Akynezo FDC) 20 mL liquid formulation, undiluted and administered in 30 min (Part A).

All the scheduled samples will be collected at the given times counted from the start of the injection/infusion. However, if, for whatever reason, a premature interruption of injection/infusion is needed or if a duration longer than that initially scheduled is needed, the sampling scheduled at the end of injection/infusion is to be moved to the actual end time. Actual sampling times for each subject will be recorded in the individual CRFs. The actual sampling times should not exceed the recommended tolerance ranges presented in the following table. Any deviation outside the recommended ranges will be verified through Data Clarification Forms and, if confirmed, will be reported as protocol deviation, although it will not automatically lead to the exclusion of the concerned subjects from the PK Sets.

Table 14.5.1.2 Tolerance ranges for the scheduled blood sampling times for PK analysis

Sampling time	Tolerance range
Pre-dose (0)	Within 30 min before T or R treatment administration
2 min, 5 min, 10 min, 15 min, 20 min, 30 min	0 min
45 min, 1 h, 1.5 h, 2 h	± 2 min
3 h, 4 h, 8 h, 12 h, 24 h	± 5 min
48 h, 72 h, 96 h, 120 h, 144 h, 168 h, 192 h, 216 h, 240 h	± 60 min

Actual sampling times for each volunteer will be recorded in the individual CRFs.

Blood samples (6 mL each) for PK analysis will be collected using an indwelling catheter with switch valve during confinement. The indwelling catheter for blood collection will be placed on the contralateral arm with respect to the infusion arm. The cannula will be rinsed, after each sampling, with about 1 mL of sterile saline solution containing 20 I.U./mL Na-heparin. The first 1.5 mL of blood will be discarded at each collection time to wash the cannula out of saline

solution and avoid diluting the analyte concentrations. The remaining volume of 4.5 mL of blood will then be collected from the catheter and transferred with a syringe into K₂EDTA tubes. Blood samples will be immediately centrifuged at 1500 g for 15 min at 4° C to obtain plasma. If immediate centrifugation is not possible, blood samples will be kept on melting ice or in a refrigerator at 4° C for a maximum of 1 h. Each plasma sample will be divided at room temperature within a maximum of 4 h from blood centrifugation into 6 pre-labeled tubes: F1 and F2 (both of at least 200 µL) for the assay of fosnetupitant, N1 and N2 (both of at least 500 µL) for the assay of netupitant and its metabolites. For the collection of the 3rd aliquots (F3 and N3), the remaining plasma will be used. Plasma samples will be stored frozen at ≤-70° C (F and N aliquots) until analysis.

If any clinical assessment, such as vital sign measurement or ECG recording, is foreseen at the same time-point as blood sampling for PK analysis, blood collection will be performed at the scheduled time. Vital signs and ECG recordings for immediate safety evaluation can be performed before the pre-dose sampling and after the post-dose samplings, but inside the recommended tolerance ranges presented in [Table 14.2.1](#) and [Table 14.3.1](#). Any deviations outside the recommended time ranges will be verified through Data Clarification Forms and reported as a protocol deviation. Discrete ECGs will be extracted from the continuous monitoring by the provider before blood sampling scheduled at the same time point.

14.5.2 Analytics

The plasma concentrations of fosnetupitant, netupitant and its main metabolites will be determined at Ardena Bioanalysis BV, the Netherlands, using validated liquid chromatography-tandem mass spectrometry (LC-MS/MS) bioanalytical methods with appropriate lower limits of quantification (LQL).

Analyses will be performed according to the general Principles of "OECD Good Laboratory Practices for testing of chemicals" C(81) 30 (final) and GCP.

The analytical reports will be attached to the final report.

14.5.3 Labelling, storage and transport of samples

14.5.3.1 Samples labelling Please modify as applicable

Each sample tube will be clearly and unequivocally identified with a label resistant to the storage temperature and reporting:

Study code	Study CRO-PK-22-363 - Sponsor code PNET-22-08
Subject number	001-066 (for Part A); 101-140 (for Part B)
Tube identification	F1, F2, F3, N1, N2, N3,
Study Part	Part A/ Part B
Period	1 or 2 (Part B only)
Scheduled sampling time	as min or h; see § 14.5.1

14.5.3.2 Samples storage and transport

At the Phase I Unit, aliquots N1, N2, N3, F1, F2 and F3 will be stored at $\leq 70^{\circ}\text{C}$. At the end of each collection day, the aliquots will be stored in 2 separate freezers.

All aliquots 1, packed in sufficient solid CO₂, will be shipped by an authorized courier from CROSS Research S.A. Phase I Unit, Switzerland, to Ardena Bioanalysis BV, the Netherlands. Aliquots 1 will remain stored at the laboratory for a maximum time of 3 months after a QA audited bioanalytical report is issued. Afterwards, the samples will either be destroyed or returned or stored for a longer period in agreement with the Sponsor. In case the sample destruction is chosen, a certificate of destruction will be provided to the Sponsor.

The back-up samples (aliquots 2 and 3) will remain stored at CROSS Research S.A., Switzerland. These samples could either be:

- sent to the laboratory for reanalysis, should this become necessary for analytical reasons or if any problems occur during the delivery or analysis of aliquots 1, or
- destroyed at an authorized site, or
- transferred to the Sponsor upon written request, or
- stored at CROSS Research S.A., for a maximum time of 5 years

No analyses different from those stated in this protocol and agreed by the subjects when signing the informed consent form will be performed unless a new informed consent and a new approval from the Ethical Committee is obtained. The subjects may ask to destroy their own samples at any time.

14.6 Total number of samples and blood withdrawn

During the study the following volume of blood will be collected from each subject, in the relevant study part:

For routine (safety) laboratories analysis of Part A:

Screening visit:	12 mL
Final visit/ETV:	12 mL

For routine (safety) laboratories analysis of Part B:

Screening visit:	12 mL
End of period 1:	12 mL
Confinement for period 2:	12 mL
Final visit/ETV:	12 mL

For PK analysis:

Part A:	from a minimum of $11 \times 6 \text{ mL} = 66 \text{ mL}$ to a maximum of $16 \times 6 \text{ mL} = 96 \text{ mL}$, depending on durations of injection tested in the cohorts
Part B:	from a minimum of $20 \times 2 \times 6 \text{ mL} = 240 \text{ mL}$ to a maximum of $(20 \times 6 \text{ mL}) + (25 \times 6 \text{ mL}) = 270 \text{ mL}$, depending on the injection duration

The maximum total volume of blood which could be withdrawn from each subject in part A will be 120 mL (safety + PK analyses), over a maximum study duration of 28 days.

The maximum total volume of blood which could be withdrawn from each subject in part B will be of 318 mL (safety + PK analyses) over a study duration of 55 days or longer. In either case the total volume of blood withdrawn will not exceed a standard blood donation.

15 ASSIGNMENT OF STUDY TREATMENT

15.1 Randomization

Cohorts of Part A are not randomized.

The randomization lists for Part B will be computer-generated by the Biometry Unit of the CRO, using the PLAN procedure of SAS® version 9.3 (TS1M1) (13) or higher (the actual version will be stated in the CSR). The randomization list will be attached to the final CSR.

15.2 Treatment allocation

In cohort 1 of Part A, the subjects will be assigned to one parallel treatment (T or Ra) according to their admittance to the Phase I Unit, i.e., the first 10 subjects will receive Ra and the next ten T. In study part B, the subjects will be assigned to one of 2 sequences of treatments (e.g., T-R or R-T) according to their randomization number that will be given to the subjects on study Day -1, period 1.

The treatments will be assigned to the subjects through opaque sealed envelopes. Each envelope will report the randomization number on the label and the treatment inside and it will be opened at the time of randomization for each patient. The randomization letters will be generated through a dedicated SAS program based on the randomization list. The Investigator or his deputy in charge of the randomization number assignment will have no access to the complete randomization list, thus being unaware of the sequences corresponding to each randomization number.

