Dose regimens: Part A of the study: In cohort 1, 10 healthy volunteers (HV) will receive a dose of T as a one single 30-min IV infusion and additional 10 subjects will receive a single IV dose of undiluted R (treatment Ra) as a one single 30-min IV infusion of 20 mL, according to a parallel group design. In each of 3 consecutive cohorts - 2, 3 and 4, - 10 healthy volunteers (HV) will receive a single IV dose of T and will be sequentially treated as subgroups of 3, 3, and 4 subjects, respectively. A staggered approach with decreasing infusion time duration will be applied to the injection of T in cohorts 2, 3 and 4. Therefore, in each cohort, the T injection duration will vary as follows: Cohort 1: 30 min (T or Ra) Cohort 2: 15 min (T) Cohort 3: 5 min (T) Cohort 4: 2 min (T) At the end of cohort 1 and of each subgroup of cohorts 2, 3 and 4, safety and tolerability results will be evaluated by the Investigator and the study Sponsor Medical Expert. Predefined stopping rules will be considered for deciding about continuing with the next cohort and a shorter injection duration. If the safety data obtained from a treated cohort are considered as not sufficient for taking a decision on the infusion duration de-escalation process and if additional safety data are deemed necessary to allow such decision to be taken, the study Investigator and the Sponsor Medical Expert may decide to add additional subjects (up to a maximum of 4 subjects per cohort) to the 10 subjects of the treated cohort. After cohort 1, if the injection duration of 30 min of T proves to be safe and well tolerated, 15 min will be tested in cohort 2. After cohort 2, if the injection duration of 15 min proves to be safe and well-tolerated, 5 min will be tested in cohort 3. After cohort 3, if the injection duration of 5 min proves to be safe and well-tolerated, 2 min will be tested in cohort 4. At the end of study Part A, the Sponsor will take a final decision whether to proceed with study Part B with the resulting shortest injection duration considered as adequate in terms of safety determined in study Part A. Part B of the study will follow a 2-way, cross-over randomized design and will include 40 male and female subjects. Before entering the crossover phase, each subject will receive P at the shortest infusion duration

STUDY SYNOPSIS (cont.)

Dose regimens (continued):

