8.6 Risks and benefits

Healthy male and female subjects will take part in the study. In Part A, each subject will receive one single injection of 20 mL of IV fosnetupitant at decreasing infusion durations from 30 min to 15, 5 and 2 min in the respective study cohort or a 30-min infusion of the 20 mL (undiluted) IV Akynezo FDC (R α treatment limited to 10 subjects in cohort 1). Different subjects will be treated in each cohort. In Part B, following a 20-mL saline solution for infusion administered as placebo at the infusion duration established in study Part A, new subjects will receive in 2 study periods a single administration of the 20 mL IV fosnetupitant solution (T, test treatment) at the infusion duration established in study Part A and a single 20 mL IV Akynezo infusion diluted to 50 mL and administered in 30 min (R, reference treatment), according to a cross-over design.

Blood sampling with cannula insertion and repeated venipuncture may cause minor discomfort. The risks associated with blood draws include pain, bleeding and bruising.

No specific benefits for the healthy subjects participating in the current study are foreseen except for the medical screening. Subject remuneration will be paid to each participating subject after study completion. The remuneration covers loss of time and any inconvenience caused by the participation in the study.

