10.1.2 Dose regimen

Part A of the study:

In cohort 1, 10 healthy volunteers (HV) will receive a dose of T as a one single 30-min IV infusion and additional 10 subjects will receive a single IV dose of undiluted R (defined as R_a) as a one single 30-min IV infusion, according to a parallel group design. In each of 3 consecutive cohorts (cohorts 2, 3 and 4), 10 healthy volunteers (HV) will receive a single IV dose of T at a predefined infusion duration and will be sequentially treated as 3 subgroups of 3, 3, and 4 subjects, respectively.

A staggered approach with decreasing infusion time duration will be applied, from cohort 1 to cohort 4, to the administration of T, as follows:

Cohort 1: 30 min

Cohort 2: 15 min

Cohort 3: 5 min

Cohort 4: 2 min

At the end of cohort 1 and of each subgroup of cohorts 2, 3 and 4, safety and tolerability results will be evaluated by the Investigator and the study Sponsor Medical Expert. Predefined stopping rules will be considered for deciding about continuing with the next cohort treatment and a shorter injection duration of T (see § 13.2). Predefined stopping rules are applicable for subjects treated with T. After cohort 1, if the injection duration of 30 min proves to be safe and well tolerated, 15 min injection duration will be tested in cohort 2. If the injection duration of 15 min proves to be safe and well-tolerated, 5 min injection duration will be tested in cohort 3. If the injection duration of 5 min proves to be safe and well tolerated, a 2 min injection will be tested in cohort 4. If the safety data obtained from a treated cohort receiving T are considered as not sufficient for taking a decision on the infusion duration de-escalation process, and if additional safety data are deemed necessary to allow such decision to be taken, the study Investigator and the Sponsor Medical Expert may decide to add additional subjects (up to a maximum of 4 subjects per cohort) to the 10 subjects of the treated cohort.

Part B of the study will follow a 2-way, cross-over randomized design and will include 40 subjects.

All the subjects will receive one single IV dose of P (placebo, as 0.9% NaCl solution for infusion) in period 1, at the infusion duration selected in study part A.

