15.3 Blinding

This is an open-label study. No masking procedure will be applied.

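### In cohort 1 of Part A, T and Ra are filled one block after the other, so the descriptive T–Ra summaries are fully confounded with admission order (low impact, cheap to improve)

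*Protocol*

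**What the plan says.** The synopsis gives cohort 1 as 10 subjects on T and 10 on Ra, the latter "as a one single 30-min IV infusion of 20 mL, according to a parallel group design". Section 10.1.2 repeats the label: "according to a parallel group design". Section 15.1 states: "Cohorts of Part A are not randomized". Section 15.2 gives the rule. Subjects are assigned in order of admission: "the first 10 subjects will receive Ra and the next ten T". Section 15.3 adds: "This is an open-label study. No masking procedure will be applied".

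Ra appears nowhere else in the study; section 8.6 describes it as "treatment limited to 10 subjects in cohort 1". On the use of the results, section 10.1.2 says: "Predefined stopping rules are applicable for subjects treated with T". Section 9.1.2 makes description of the PK after T and after Ra a secondary objective of Part A. Section 17 says that measured parameters will be evaluated and compared by descriptive statistics, and section 17.5.1 tabulates treatment-emergent adverse events by treatment.

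**The concern.** Within cohort 1, T and Ra share the fosnetupitant dose (235 mg), the volume (20 mL undiluted) and the duration (30 min). They differ in product, including the palonosetron that Ra contains. No other contrast in the study holds these features constant. In Part B, T is given undiluted and R is diluted to 50 mL, so product is mixed with dilution there, and with duration as well unless 30 min is the duration selected.

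A reader of the report will see T at 30 min beside Ra in the PK and adverse event tables and may take the difference as a product effect. With all Ra subjects admitted before all T subjects, such a difference could equally reflect who was admitted early or a change over calendar time. The stake is the interpretability of those descriptive summaries.

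**Working it through.** The protocol gives no power, margin or error rate for cohort 1, and section 17.2 says its size was not derived statistically. There is therefore no stated figure to reproduce. The check is how strongly the rule ties treatment to admission order.

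**Inputs**

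- Cohort 1: 10 Ra and 10 T (synopsis; 10.1.2).
- Rule: admission ranks 1–10 receive Ra and ranks 11–20 receive T (15.2).
- No randomisation in Part A (15.1). No alternation, stratification or adjustment for admission order is stated.

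**Gap in mean admission rank, T minus Ra**

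- Protocol rule: mean of 11–20 minus mean of 1–10 = 15.5 − 5.5 = 10.0. This is the ten largest ranks against the ten smallest, so no split of 10 and 10 can exceed it. The correlation of treatment with rank is 0.87. Its correlation with first or second block is exactly 1.
- Strict alternation, for reference: 11 − 10 = 1.0, correlation 0.09.
- 1:1 randomisation: expected gap 0. The variance of ranks 1–20 (divisor N − 1) is 20 × 21/12 = 35, so the SD of the gap is √(35 × (1/10 + 1/10)) = √7 ≈ 2.6. A simulation of 50,000 permutations gave 2.63.
- Chance that randomisation produces a split as extreme as the protocol's, in either direction: 2/C(20,10) = 2/184,756 ≈ 0.00001.

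**What this means for a T–Ra difference**

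Suppose, as an assumption, that an outcome drifts by d per admission position. The protocol gives no value for d; it may be zero or of either sign. The T–Ra difference is then shifted by 10d under the protocol rule, by d under strict alternation and by 0 on average under randomisation. For a step change of size s between the 10th and 11th subject, the protocol rule puts all of s into the T–Ra difference, while randomisation puts in 0 on average.

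These figures measure how far treatment is aligned with order. They do not measure a bias that is known to exist.

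**Does any decision use the contrast?**

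- Stopping rules (10.1.2, 13.2.2): counts of events related to T, within a cohort. Ra is not used.
- Choice of duration (13.2.2): safety and tolerability of T. Ra is not used.
- Equivalence (17.4.2): ANOVA and 90% CI on Part B data only.
- Descriptive PK and adverse event summaries (9.1.2, 17, 17.5.1): T and Ra both appear. This is the only place where the confounding matters.

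**The case against.** The strongest reply is that nothing in the plan rests on this contrast. Ra is there to describe the PK of undiluted Akynzeo (8.5, 9.1.2). The figure in section 4 labels the PK of Part A as exploratory. No T–Ra hypothesis, margin or ratio is given, and tabulating events by treatment is routine reporting. All cohort 1 subjects are healthy volunteers under the same entry criteria, and the duration cohorts of Part A are also sequential by design. All of this stands, and it is why the impact is low. It does not remove the point: section 17 expects descriptive comparison, the tables will set T beside Ra, and a statistical analysis plan cannot undo an alignment fixed by the allocation rule.

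A reader might infer stronger things that the protocol does not support:

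- *That the parallel-group label contradicts the sequential rule.* It does not. A parallel-group design means that each subject receives one treatment; it does not imply randomisation, and 15.1 says openly that Part A is not randomised.
- *That admission staff could steer subjects to a treatment, or that samples are assayed in batches matching the blocks.* The treatment of the next subject is predictable, but the protocol describes no selection by staff and no assay by admission block.
- *That a safety check is missing between Ra and T.* That is a separate matter. It has no bearing on confounding, and randomising the cohort would not create such a check.

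**Conclusion.** The point holds as a low-impact improvement. In cohort 1, treatment and admission block coincide for all 20 subjects, so a T–Ra difference in PK or adverse events cannot be separated from an effect of admission order. This follows from 15.2 alone and needs no outside assumption. Whether there is any order effect, and how large, cannot be determined from the protocol.

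A reader might go on to conclude that the selected duration or the equivalence result is at risk. The protocol does not support that: the stopping rules and duration selection concern T, and equivalence is tested in a separate randomised crossover with different subjects. What remains is a weak but disclosed allocation rule that limits one set of descriptive summaries and is easily avoided.

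**What to change.** Randomise the 20 cohort 1 subjects 1:1 to T or Ra, using the SAS PLAN list and sealed envelopes that 15.1 and 15.2 already set out for Part B, and amend those two sections. The cost is a 20-line list, 20 envelopes and about two sentences. No sample size changes. The one downside is that Ra subjects would no longer all be dosed before T subjects, an order for which the protocol gives no reason and to which it attaches no decision.

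If the Ra-first order is deliberate, keep it, give the reason in 15.2, and state that T and Ra will be described separately with no comparison drawn. If cohort 1 has already been dosed, only that statement remains possible.
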